## 2. Background

### 2.1. Regarding primary objectives:

Counseling and provision of postpartum contraception is an integral component of comprehensive reproductive healthcare. A woman's preference for contraception is paramount; early initiation of postpartum contraception may assist in optimal birth spacing promoting the wellbeing of mother and baby (1). Equally important is the provision of appropriate support for breastfeeding (1). Exclusive breastfeeding for six months with continuation beyond one year of age is recommended by the American Academy of Pediatrics (AAP) (2), American Academy of Family Physicians (3), American College of Obstetricians and Gynecologists (ACOG) (4), and the World Health Organization (WHO) (5). In the United States, approximately 47% and 25% of women breastfeed exclusively at three and six months respectively, and 57% and 36% of women who supplement with formula continue breastfeeding at three and six months respectively (6).

Current recommendations advise against use of combined hormonal contraceptives in the first 4-6 weeks postpartum due to the hypercoagulable state of pregnancy and the high risk for thrombogenic events (7). Progestin-only hormonal contraceptive methods are considered appropriate for initiation in the postpartum period including the ENG subdermal implant, the levonorgestrel intrauterine device (LNG IUD), and the depot medroxyprogesterone acetate injection (8). However, because lactogenesis is precipitated by progesterone withdrawal after placental expulsion, early initiation of progestin-containing

**PROTOCOL TITLE:** Effect of immediate versus standard postpartum insertion of the contraceptive implant on breastfeeding outcomes

**2.2. Regarding primary objectives:**

A systematic review identified 50 studies of progestin-only contraception and breastfeeding (13). These studies can be divided into those that focus on breastfeeding performance (initiation, continuation, and exclusivity) and those that focus on infant health and growth. Fewer than ten studies focus on use of the contraceptive implant and breastfeeding performance, of which only two measure outcomes related to immediate insertion versus standard insertion (5,12). In Guttcheff et al., a RCT in healthy postpartum women was performed to evaluate time to lactogenesis stage II between early ENG implant insertion (1-3 days

**PROTOCOL TITLE:** Effect of immediate versus standard postpartum insertion of the contraceptive implant on breastfeeding outcomes

postpartum (PP)) and standard insertion (4-8 weeks PP). The authors demonstrated that early insertion is non-inferior to standard insertion with a mean difference of 1.4 hours. In addition, no differences were found between the early insertion group and standard insertion group for incidence of lactation failure, breastfeeding, formula supplementation and breastfeeding continuation at 6 months. Bryant et al., studied immediate (before leaving the hospital) versus standard (at 6 weeks PP) insertion of the ENG implant in adolescent and young women age 14-24 years old. Their primary outcome was contraceptive use at six months. No difference was found in contraceptive use between the two groups at six months. The rate of lactation continuation at three and six months was higher in the immediate insertion group.

**2.3. *Regarding primary objectives:***

Prior studies lack specific data on timing of early postpartum implant use and the effect on breastfeeding. The contribution of the proposed research is to add to the limited literature on immediate postpartum contraception options and, specifically, to evaluate the impact of initiating ENG implants within the first 24 hours on breastfeeding continuation. The lack of precise timing for immediate postpartum progestin initiation was cited as an important research gap in the US MEC (8). Additionally, more and more state Medicaid programs are reimbursing for implant insertion prior to the hospital discharge (16). It is important to make sure that this increasing trend is supported by the best possible evidence.

**Regarding secondary objectives:**

1. Bleeding patterns: Irregular bleeding is the most common side effect noted by users of the ENG contraceptive implant. Limited evidence shows that this holds true in the postpartum period (17). In a retrospective cohort study of women who underwent immediate versus standard postpartum insertion of the implant, approximately one in five women requested discontinuation of use due to irregular bleeding, and this rate was not significantly different between the two groups (17). Evidence on the effect of immediate postpartum insertion of the ENG contraceptive implant on lochia is limited and mixed. An RCT of immediate versus standard postpartum insertion of the six-rod levonorgestrel implant showed significantly more total days of bleeding for the immediate insertion group (18), while a more recent Australian prospective cohort study demonstrated no lengthening of the duration of lochia (postpartum bleeding) with immediate insertion (19). We will measure postpartum bleeding patterns using periodic review of a patient bleeding diary that quantifies bleeding on a daily basis as “none”, “spotting”, “bleeding” or “heavy bleeding”. As patient dissatisfaction with irregular bleeding likely mediates discontinuation for this reason, we will also measure patient satisfaction with their bleeding pattern postpartum.

PROTOCOL TITLE: Effect of immediate versus standard postpartum insertion of the contraceptive implant on breastfeeding outcomes

2. Postpartum mood changes: It is possible that postpartum use of an ENG implant may affect postpartum mood. In a retrospective study of adverse event reporting for ENG implant use, it was noted that postpartum depression was a commonly reported adverse event, and therefore may be associated with implant use in the postpartum period (20). In addition, in a secondary analysis study, use of the ENG implant in the postpartum period was associated with a higher risk of later antidepressant use compared to women with no hormonal contraceptive use (21). Women's perception of contraceptives' effect on their mood is a significant factor in contraception discontinuation (22). We hypothesize that timing of implant insertion will not increase postpartum depression related mood changes as measured by the EPDS. We will also assess patient perception of impact of ENG implant insertion on mood.
3. Postpartum sexual function: Effect of postpartum ENG implant use on postpartum sexual function is not well studied. However, in a 2016 study of impact of LARC use on sexual function (not in the postpartum period), it was noted that there was no objective change in sexual function with initiation of copper IUD, levonorgestrel IUDs or ENG implant (24). We hypothesize that this is also true in the postpartum period and that the effect of timing of ENG implant insertion will not affect postpartum sexual function as measured by the FSFI. The FSFI is a validated tool for assessing female sexual function that been used in the aforementioned studies, both in assessing LARC effects and in the postpartum period (25). Patient perceptions of the effect of their contraceptive on sexual experience may affect contraceptive continuation rates regardless of objective findings on sexual function. In a 2018 study of the impact of sexual function and perceived effect of contraceptive method on sexual experience on continuation rates of multiple LARCs, patients' perception of a negative impact of the contraceptive on sex life was the strongest predictor of discontinuation (26). We will assess patient centered perception of impact of ENG implant insertion on sexual function.
4. Postpartum exclusive breastfeeding through 6 months postpartum: Receiving only breast milk is known as exclusive breastfeeding (EBF). AAP and WHO promote EBF for the first six month of life of infants because it provides multiple health benefits to babies and to the mother (1,5). Nationally, 46.9 % and 24.9% of women exclusively breastfeed at 3 and 6 months, respectively; in New Mexico 53.0% and 27.6% breastfeed exclusively at 3 and 6 months, respectively (6). Since this data does not provide information about the mothers who use contraception and how many of the exclusively breastfeed, we will assess this information.

**PROTOCOL TITLE:** Effect of immediate versus standard postpartum insertion of the contraceptive implant on breastfeeding outcomes

5. Factors associated with breastfeeding discontinuation: As mentioned previously, EBF is recommended for 6 months postpartum by the AAP and WHO. It is important to identify and acknowledge these factors to work and plan for counseling and initiatives to improve the length of lactation period. These factors can vary depending of society, culture and even mother's perception. Li et al reported the most common reasons for breastfeeding discontinuation during the first year postpartum were mothers' perception that their infant was not satisfied by breast milk alone and concerns about lactation and nutrition issue. In addition, mothers reported nipple biting and perceived infant loss of interest in breastfeeding (27). Odom et al, found in their study that factors such as difficulties with lactation, infant nutrition and weight, effort to pumping milk, among many others, play an important role in the decision making for lactation cessation (28). With this study, we aim to assess the reason for discontinuation in the mothers who use the implant as a contraceptive method.
6. Satisfaction with postpartum contraception counseling: The American College of Obstetricians and Gynecologists (ACOG) stated in Committee Opinion number 736: Optimizing Postpartum Care that as part of comprehensive postpartum care acknowledging women's reproductive life plan is of vital importance for decision making regarding contraception (1). We aim to explore by a survey how women perceived the counseling: if she understood the counseling and received enough information and time to make a decision about contraceptive choice. This might help to understand women's perception of counseling about postpartum contraception and may be helpful in improving current counseling.
7. Satisfaction with timing of contraceptive implant insertion: Early initiation of a contraceptive method has been recommended as an alternative by ACOG (1). This is because it has been proven that many women miss or do not have a postpartum follow up visit and it is more convenient for women to initiate a method early. When a contraceptive method is started in the postpartum period, it contributes to birth spacing, and maternal and infant wellbeing. We look to understand the satisfaction with having an implant inserted early vs having it inserted in the standard time.

### **3. Study Design**

- 3.1. This RCT will be performed at the University of New Mexico Hospitalits affiliated clinics and the University of Utah and its affiliated clinics. The study design was chosen as the gold standard for determining cause and effect; it is methodologically strong and feasible for our research questions. RCTs minimize bias such as that related to treatment assignment (e.g., selection bias and confounding).

**PROTOCOL TITLE:** Effect of immediate versus standard postpartum insertion of the contraceptive implant on breastfeeding outcomes

The two study groups will include women randomized to immediate (within 24 hours postpartum) versus standard (4-6 weeks postpartum) ENG implant insertion. The primary study endpoint is any breastfeeding at eight weeks postpartum; we will also measure breastfeeding continuation at 2, 4, 8, 12 and 24 weeks postpartum. Participants will be pregnant women 13 years old and older, who desire the ENG implant as a postpartum contraceptive and are willing to be randomized to immediate implant insertion (within 24 hours postpartum) versus standard insertion (4-6 weeks postpartum). A total of 150 participants, 75 in each group, will be enrolled to ensure adequate power to determine the primary outcomes, after anticipated loss to follow up.

#### **4. Inclusion and Exclusion Criteria**

4.1. Potential participants may be identified in the following locations/timeframes: 1) antenatal clinics, 2) visits to OB-Triage 2) on admission to L&D for delivery not in active labor or 4) during the first postpartum hours in the Ob-Gyn ward of the UNM Hospital and University of Utah Hospital.

- When women decide on an implant as a postpartum contraceptive in any of these venues, the PCP (Ob-Gyn, Family Medicine physicians/residents and midwives) may discuss the patient's interest in hearing about the study and may contact the research coordinator by a message in the EMR or by phone or in person to let her know that the patient is interested in hearing about the study.
- Additionally, the research coordinator will review antenatal clinic, OB Triage and inpatient (L&D and postpartum) lists to assess patients' contraceptive plan through review of the EMR.
- If the patient expresses interest, the research coordinator and/or a study co-investigator will explain the study, screen the patient for eligibility and obtain informed consent.
  - *Note: Hepatitis C will not be considered an exclusion criterion. Mothers with Hepatitis C can breastfeed per the Centers for Disease Control and Prevention. However, HCV is spread by infected blood. Therefore, if the HCV-positive mothers' nipples and/or surrounding areola are cracked and bleeding, she should stop nursing temporarily. To maintain her milk supply while not breastfeeding, she can express and discard her breast milk until her nipples are healed. Once her nipples are no longer cracked or bleeding, the HCV-positive mother may fully resume breastfeeding. If we identify a mother with hepatitis C, we will assess through follow up questionnaires when they stopped breastfeeding, if they continued to express milk during the period of no lactation and when they restarted lactation.*
  - *Note: We will continue enrollment in the study for all women regardless of the infants' status; we will perform a secondary sub-group analysis of women/infants with complications in order to improve the ability to generalize from the study.*

We request a waiver of HIPAA for screening/recruitment purposes.

**PROTOCOL TITLE: Effect of immediate versus standard postpartum insertion of the contraceptive implant on breastfeeding outcomes**

**4.2. Inclusion Criteria**

- Pregnant women or women who have delivered vaginally and by cesarean section within 22 hours (2 hour window will allow for implant insertion by 24 hours postpartum)
- Aged 13 and older
- English or Spanish speakers
- Deliver an infant at UNM or Utah Hospital at  $\geq$  37 weeks gestational age
- Intend to breastfeed
- Desire the implant as a method for contraception
- Agree to randomization
- Must have a working phone (study questions to be answered through phone calls or accessed electronically by a link sent through email or text message)

**Exclusion Criteria**

- Under age 13
- History of breast cancer (screen by past medical history)
- History of undiagnosed vaginal bleeding (screen by past medical history)
- Head trauma that affected pituitary function (screen by past medical history)
- Prolactin insufficiency (screen by past medical history)
- Previous lactation failure (defined as no lactation within 5 days postpartum)
- Any contraindication to lactation/implant use including diseases transmittable by breast milk (screen by past medical history)
- Liver dysfunction (screen by past medical history)
- Use of drugs that inhibit lactation (screen by medical history)
- Sensitivity to the components of the ENG implant (screen by past medical history)
- Contraindications to use the implant by the (US MEC) (screen by past medical history)
- Active labor
- Delivery at  $<$  37 weeks gestational age

There is a description of different inclusion/exclusion criteria between the sites. UNM Is recruiting minors under age 18 and over the age of 13, and the University of Utah is not recruiting minors. This is the only difference in the protocols.

4.3. This study will include pregnant adolescent and adult women. This study will not recruit adults who are unable to consent or women who are incarcerated.

4.4. This study will recruit women who can speak and read English and/or Spanish fluently.

**5. Number of Subjects**

5.1 NA

PROTOCOL TITLE: Effect of immediate versus standard postpartum insertion of the contraceptive implant on breastfeeding outcomes

5.2. This is a multi-site study. Through the University of New Mexico Hospital, its affiliated clinics and the University of Utah and its affiliated clinics. We will recruit up to 200 participants between both study sites.

5.3. Up to 200 participants will be enrolled, with a goal of 75 in each group, to ensure adequate power to determine the primary outcome, after anticipated loss to follow up.

This study is a non-inferiority trial designed to demonstrate that immediate postpartum insertion of the ENG implant is non-inferior to standard ENG implant insertion with respect to the proportion of women who discontinue breastfeeding by 8 weeks after delivery. Discontinuation of breastfeeding under the current treatment, standard insertion, is expected to be 30% based on previous studies (10, 15). To achieve 80% power with a 1-sided Type 1 error of 5% utilizing the Z test (unpooled), 62 participants are required in each group for a total of 124. Accounting for expected loss to follow up of 20%, the total number of participants required is 149, rounded to 150. We intend to enroll up to 200 participants due to unanticipated loss to follow up, so this should ensure that we have enough data for data analysis.

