## 13.Data Analysis

13.1 We will conduct a primary analysis per protocol and a secondary analysis per intention to treat. The rationale behind this strategy is to analyze both approaches and examine the result for consistency. A Repeated measures ANOVA analysis will be used for continuation of breastfeeding. To evaluate secondary outcomes between the two

**PROTOCOL TITLE:** Effect of immediate versus standard postpartum insertion of the contraceptive implant on breastfeeding outcomes

groups we will use the T-test, Wilcoxon Rank Sum test, Chi-squared test, or Fisher's exact test as appropriate. Secondary outcomes to be evaluated are to compare time of exclusivity of breastfeeding, mix breastfeeding, factors associated with discontinuing breasts feeding, time of breastfeeding discontinuation and patient satisfaction with postpartum contraception counseling and with timing of placing the implant between both groups. If there are significant differences between treatment groups, multivariable linear (for continuous outcomes) and logistic (for dichotomous outcomes) regression will be utilized in addition to control for confounding.

13.2 This study is a non-inferiority trial designed to demonstrate that immediate postpartum insertion of the ENG implant is non-inferior to standard ENG implant insertion with respect to the proportion of women who fail to breastfeed by 8 weeks after delivery. The failure rate for continuation of breastfeeding under the current treatment, standard insertion, is expected to be 30%.

The following sample size determination and plan for data analysis was developed in conjunction the University of New Mexico Clinical and Translational Science Center (CTSC). The non-inferiority margin for both primary outcomes is 15%, meaning that immediate insertion can be regarded as non-inferior (in terms of breastfeeding continuation) to standard insertion if the difference in rate with immediate insertion is no more than 15% worse than with standard insertion. To achieve 80% power with a 1-sided Type 1 error of 5% utilizing the Z test (unpooled) 62 participants are required in each group for a total 124. Accounting for the expected loss of follow up of 20%, the total subjects 149, round to 150. We intend to enroll up to 200 participants due to unanticipated loss to follow up, so this should ensure that we have enough data for data analysis.

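### The 20% loss allowance multiplies 124 by 1.2 instead of dividing by 0.80, so the enrolment goal of 150 leaves 120 evaluable women, 4 short of target (a minor arithmetic error)

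*Combined protocol and SAP*

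**What the plan says.** Section 5.3 gives the evaluable requirement: "62 participants are required in each group for a total of 124". The design inputs around it are: "To achieve 80% power with a 1-sided Type 1 error of 5% utilizing the Z test (unpooled"; and "Discontinuation of breastfeeding under the current treatment, standard insertion, is expected to be 30% based on previous studies (10, 15". The margin is in section 13.2: "The non-inferiority margin for both primary outcomes is 15" (in per cent).

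The allowance for loss follows in section 5.3: "Accounting for expected loss to follow up of 20%, the total number of participants required is 149, rounded to 150". Section 13.2 has the same step: "Accounting for the expected loss of follow up of 20%, the total subjects 149, round to 150". Section 3.1 turns the result into the recruitment figure: "A total of 150 participants, 75 in each group, will be enrolled to ensure adequate power", and says that this already allows for the loss expected.

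Section 5.3 also sets a goal of 75 per group. The cost table in section 22.1 lists 75 immediate and 75 standard insertions. Sections 5.2, 5.3 and 13.2 allow enrolment to go as high as 200. In 5.3 and 13.2 the reason given is loss beyond what was anticipated. Section 3.1 does not mention 200.

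**The concern.** An expected loss of 20% means that 80% of the women enrolled are available for analysis. The number to enrol is therefore the evaluable target divided by 0.80. Multiplying by 1.20 adds 20% of the evaluable number, whereas the loss is 20% of the larger enrolled number, so the allowance is always too small. The figure 149 matches the multiplication and not the division.

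What is at stake is whether the plan is internally consistent. If the team stops at its goal of 75 per group and sees exactly the loss it predicted, it falls below the evaluable number that it says it needs for 80% power. Anyone who checks that one sentence will find the discrepancy.

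**Working it through.** **Inputs.** Evaluable target 62 per group, 124 in total (5.3, 13.2). Loss 20% (5.3, 13.2). Enrolment goal 150, 75 per group (3.1, 5.3). Ceiling 200 (5.2, 5.3, 13.2). Control discontinuation 30% (5.3, 13.2). Margin 15 percentage points (13.2). One-sided 5%, 80% power, unpooled Z test (5.3, 13.2).

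**1. Reproduce the plan's figure.** n × (1 + d) = 124 × 1.2 = 148.8, rounded up to 149, then 150. This matches the plan.

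**2. Inflate for a loss of 20% of those enrolled.** n / (1 − d) = 124 / 0.80 = 155. Per group, 62 / 0.80 = 77.5, rounded up to 78, so 156 with equal arms.

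**3. Work backwards from possible enrolments at 20% loss.**

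| Enrolled | Evaluable (× 0.80) | Against 124 |
|---|---|---|
| 149 | 119.2 | about 5 short |
| 150 | 120 (60 per group) | 4 short |
| 155 | 124 | met |
| 156 | 124.8 | met |
| 200 | 160 (80 per group) | met, 36 over |

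The largest loss that still leaves 124 is 1 − 124/150 = 17.3% at 150 enrolled, and 1 − 124/200 = 38% at 200.

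**4. Cost in power.** This needs the true rates. The documents give 30% for standard insertion and nothing for immediate insertion. The unpooled non-inferiority formula per group is

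n = (1.645 + 0.842)² × [p_S(1 − p_S) + p_I(1 − p_I)] / (0.15 + p_S − p_I)²,

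where p_S and p_I are the discontinuation proportions with standard and immediate insertion.

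- 30% versus 25%: 6.183 × (0.21 + 0.1875) / 0.20² = 61.4, so 62. This reproduces the plan.
- 30% versus 30%: 6.183 × 0.42 / 0.15² = 115.4, so 116. This does not.

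With equal rates, 62 also results from a margin of about 20.5 points. The documents state neither that margin nor the 25% rate.

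Power is Φ[(0.15 + p_S − p_I) / SE − 1.645], with SE the square root of [p_S(1 − p_S) + p_I(1 − p_I)] / n. At 30% versus 25%:

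- 62 per group: SE = √(0.3975/62) = 0.0801; 0.20/0.0801 − 1.645 = 0.853; power 80.3%.
- 60 per group: SE = √(0.3975/60) = 0.0814; 0.20/0.0814 − 1.645 = 0.812; power 79.2%.

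The slip costs 80.3 − 79.2 = 1.1 points.

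**The case against.** The strongest defence is the ceiling. The sentence after the one at issue, in both 5.3 and 13.2, says that enrolment may go to 200 so that enough data are available. At 20% loss that leaves 160 evaluable women. This stands as a practical mitigation: a team that uses the headroom will not miss 124 because of this slip. It does not make the stated figure right. The ceiling is a maximum, justified by loss beyond expectation, while the expected 20% is meant to be covered by the 149/150. The goal stays at 75 per group, and 3.1 gives 150 alone.

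Actual loss on the primary endpoint may also be below 20%. Section 12 provides a retrospective survey and chart review, extending to the infant's chart, to recover feeding status. That is possible, but withdrawals under section 15 could push the other way, and the plan's own working figure is 20%.

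Three stronger readings are tempting and are not supported:

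- **A reader might infer that this error leaves the trial underpowered.** It accounts for about one point of power, and the permitted ceiling more than absorbs it.
- **A reader might infer that 80% power is missed even under the assumption kindest to the plan.** The 25% versus 30% case merely reproduces 62. At 20% versus 30%, 60 per group gives Φ[0.25/√(0.37/60) − 1.645], about 94%.
- **A reader might attribute to this slip the low power with both arms at 30%.** That power is 55.9% at 60 per group, but already about 57% at 62. Nearly all of the gap to 80% comes from the unstated true difference behind 62.

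**Conclusion.** The point holds as a minor arithmetic error. The figure of 149 in 5.3 and 13.2 is wrong on the plan's own inputs. It should be 155, or 156 with equal arms, and the 150 in 3.1 inherits the error. At the stated goal and stated loss the plan ends 4 women below its own target. That conclusion needs only the 124 and the 20%, with the 20% read as a share of the women enrolled.

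The size in power, 79.2% against 80.3%, also depends on the 25% versus 30% assumption, which the documents do not state.

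Correcting this step does not endorse 62 per group. With both arms at 30%, the stated inputs need 116 per group: 232 evaluable, and 232 / 0.80 = 290 enrolled, which is above the ceiling of 200. That is a separate and larger issue.

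**What to change.** - **Sections 5.3 and 13.2:** replace the 149-rounded-to-150 figure with 124 / 0.80 = 155, rounded up to 156 (78 per group).
- **Dependent figures:** align the 150 and 75 per group in 3.1, the goal of 75 per group in 5.3, and the two entries of 75 in the section 22.1 cost table. Section 13.2 has no per-group enrolment goal to change.
- **Alternative:** keep 150, state that 120 evaluable women (60 per group) are expected at 20% loss, and give the matching power with its assumed rates.
- **Either way:** state in the same sentence the true difference assumed in deriving 62 per group, so that the corrected enrolment is not read as confirming that number.

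The cost is protocol wording and, under the first option, a goal 6 women higher. Since 156 is within the existing ceiling of 200, maximum enrolment need not rise for this correction. Resolving the basis for 62 per group may cost more and should be handled as its own point.
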